1.2.13.3. Study B1371003: Phase 1b/2 Study in Patients with AML or High-Risk MDS

This is an open-label, multicenter safety and efficacy study of glasdegib in combination with LDAC, decitabine, or intensive chemotherapy in patients with AML or high-risk MDS. This study includes two portions:

- Phase 1b: To evaluate the safety and RP2D determination of three first-line combination regimens of glasdegib plus: LDAC, decitabine, or '7+3' induction chemotherapy (cytarabine/daunorubicin).
- Phase 2: To assess the efficacy of two combination regimens:
 - A Phase 2 randomized (2:1) open-label component in unfit patients (P2 Unfit) enrolled to receive either LDAC in combination with glasdegib or LDAC alone;
 - A Phase 2 single arm component in fit patients (P2 Fit) to receive glasdegib in combination with 7+3 induction chemotherapy. Please refer to the glasdegib IB for further details on this part of the study.

Phase 1b Part

In the Phase 1b part of Study B1371003, 52 patients with AML or higher risk MDS were treated with glasdegib 100 mg or 200 mg PO Qday in combination with LDAC (n=23), decitabine (n=7), or 7 + 3 (n=22).

In Arm A (LDAC + glasdegib), 23 unfit patients were enrolled (15 males/8 females). Seventeen (17) patients received a starting glasdegib dose of 100 mg and 6 patients of 200 mg QD. No DLTs were observed. The most frequently reported treatment-related AEs in patients were nausea (n = 6, 35.3%), diarrhoea and neutropenia (n = 5, 29.4% each), and muscle spasms and dysgeusia (n = 4, 23.5% each).

In Arm B (Decitabine + glasdegib) 7 unfit patients were enrolled (5 male/2 female). Four (4) patients received glasdegib 100 mg and 3 patients received glasdegib 200 mg. No DLTs were reported. The most frequently reported treatment-related AEs of any grade were nausea (n=3, 75%), diarrhoea, thrombocytopenia, and neutropenia (n=2, 50% each). Of the AML patients treated in combination with decitabine, 2/5 (40%) responded (1 CR and 1 complete response with incomplete blood count recovery (CRi)), a similar population of newly diagnosed elderly AML patients was enrolled into a Phase 3 study of decitabine vs supportive care vs low dose cytarabine where the CR+ CRi rate was 25.6% in the decitabine only arm (Kantarjian et al, 2012).⁵⁸ Of the high-risk MDS patients treated in combination with decitabine, 2/2 achieved a response of mCR. Median OS in the combined AML and MDS patients was 4.4 months, 11.5 months (historical mOS of 7.7 months; Kantarjian et al, 2012),⁵⁸ and 34.7 months respectively in the 3 treatment arms. This arm was not evaluated in the Phase 2 component of Study B1371003.

In Arm C (Cytarabine/Daunorubicin + glasdegib), 22 fit patients were enrolled (12 males/10 females). Sixteen patients received a starting glasdegib dose of 100 mg QD and 6 patients of 200 mg QD. The most frequently reported treatment-related AEs in patients who received glasdegib 100 mg + cytarabine + daunorubicin of any grade were nausea (n =13, 81.3%), diarrhea, febrile neutropenia and muscle spasms (n = 7, 43.8% each), dysgeusia (n = 6, 37.5%), stomatitis, headache, fatigue and pyrexia (n = 5, 31.3% each), constipation, dyspepsia, vomiting, anaemia, neutropenia, white blood cell count decreased, hypocalcaemia, hypokalaemia and alopecia (n = 4, 25% each). A DLT of Grade 4 polyneuropathy, later attributed to concomitant medication, was reported at the 100 mg dose level and treatment was permanently discontinued in that patient.

Of the 45 AML patients treated in the entire Phase 1b cohort of Study B1371003, 1/20 treated patients in combination with LDAC responded (1 CR), 2/5 treated in combination with decitabine responded (1 CR, 1 complete response with incomplete blood count recovery (CRi)), and 11/20 treated patients in combination with 7 + 3 responded (10 CR, 1 CRi).

Median OS (in AML and MDS patients combined) were 4.4 months (80% CI: 2.5, 6.6), 11.5 months (80% CI: 4.5, 17.4), and 34.7 months (80% CI: 14.5, Not Reached), respectively.

Of the 7 high-risk MDS patients treated in the entire Phase 1b cohort of Study B1371003, 2/3 treated in combination with LDAC responded (1 CR, 1 mCR), 2/2 treated in combination with decitabine responded (2 mCR), and 2/2 treated in combination with 7 + 3 induction chemotherapy responded (1 CR, 1 mCR).

Phase 2 Randomized Combination Part (Phase 2 Unfit)

In the Phase 2 portion of Study B1371003, a prospective, randomized (2:1), open-label clinical trial in 132 AML patients not suitable for intensive chemotherapy based on age or other risk factors, the addition of glasdegib 100 mg PO Qday to LDAC vs LDAC alone resulted in a significant improvement in OS (median 8.8 months (80% CI: 6.9, 9.9) vs 4.9 months (80% CI: 3.5, 6.0); HR 0.513 [80% CI: 0.394-0.666]; 1-sided p-value=0.0004 based on stratified log-rank test. This benefit in OS was also consistent within prespecified subgroups and supported by higher rates of complete remission in the LDAC + glasdegib arm (17% [80% CI: 11.9, 22.2] vs 2.3% [80% CI: 0.0, 5.2]). The addition of glasdegib to LDAC was well-tolerated, with 14 (16.7%) discontinuations due to adverse events. Thirteen of 84 (15%) patients were treated for at least 1 year (vs none in the LDAC alone arm). The median treatment duration was 83 days (range 3, 972 days) in the LDAC + glasdegib arm versus 47 days (range 6, 239 days) in the LDAC alone arm.

The safety profile was consistent with that in elderly AML patients receiving chemotherapy, namely cytopenias and gastrointestinal (GI) side effects, and had the safety/tolerability profile of other marketed SMO inhibitors. In the LDAC + glasdegib arm, serious adverse events (SAEs) of febrile neutropenia, occurred more frequently (28.6%) than in the LDAC alone arm (19.5%); however, frequencies of pneumonias were similar between treatment arms (21.4% in the LDAC + glasdegib arm and 17.1% in the LDAC alone arm), and sepsis rates were lower in the LDAC + glasdegib arm (3.6% in the LDAC + glasdegib arm and 12.2% in the LDAC alone arm). The most common AEs in the LDAC + glasdegib arm were cytopenias and GI events, consistent with that in elderly AML patients receiving chemotherapy. Cytopenias were not accompanied with higher rates of infections or bleeding as compared to the LDAC alone arm. QTcF prolongation >500 msec (Grade 3) was less frequent in the LDAC + glasdegib arm (6%) than in the LDAC alone arm (11.8%). SMO inhibitor-associated AEs in the LDAC + glasdegib arm included dysgeusia (25%), muscle spasms (21.4%) and alopecia (10.7%). In the LDAC + glasdegib arm 28 (33%) patients were permanently discontinued due to AEs vs 20 (49%) patients in the LDAC alone arm, mostly for disease progression or infection. The most common cause of death was disease progression in both treatment arms.

The safety profile and magnitude of improvement in OS appeared to be consistent with that in other ongoing single-arm studies of glasdegib as monotherapy or in combination with other chemotherapies in other MDS and AML populations.

1.2.13.4. Study B1371005: Safety and Efficacy in an Asian Population

In the ongoing Phase 1 Study B1371005, 25 Japanese patients with selected hematologic malignancies were enrolled into three cohorts: 1) Thirteen (13) patients with AML, MDS, CMML, or MF enrolled into the open label, dose escalation monotherapy cohort and received glasdegib as a single agent at doses ranging from 25-100 mg PO Qday, 2) Six (6) patients with untreated AML or high risk MDS patients unsuitable to receive intensive induction chemotherapy received glasdegib 100 mg PO QD in combination with LDAC, and 3) Six (6) untreated AML or high risk MDS patients eligible for intensive chemotherapy enrolled in combination cohort #2 and received glasdegib 100 mg PO QD in combination with cytarabine (7 days)/daunorubicin (3 days) chemotherapy.

No DLTs were observed at any dose level. The most frequently reported treatment related AEs occurring in ≥ 3 patients were: dysgeusia (69.2%), muscle spasms (38.5%), alopecia (30.8%), and decreased appetite (30.8%), blood creatinine phosphokinase increased (23.1%), constipation (23.1%), and diarrhea (23.1%). The safety and PK profiles in Japanese patients were consistent with what was observed in Western patients and in Study B1371001.

Preliminary efficacy data showed that 1 out of 7 AML patients achieved morphologic complete remission and 1 out of 4 MDS patients achieved marrow complete remission at the 100 mg dose level and 4 achieved SD across all dose levels (Yoshimoto et al, 2016).⁴⁶

1.2.14. Post Allogeneic HSCT Investigator Initiated Research Study

In an ongoing IIR, single-arm study in patients with MDS, AML, or acute lymphocytic leukemia (ALL) with evidence of minimal residual disease (MRD) or other high-risk characteristics associated with a high rate of disease relapse at the time of allo HSCT, the addition of glasdegib 100 mg PO Qday post absolute neutrophil count (ANC) engraftment for up to a year resulted in 10/13 patients free of disease relapse: 12/13 patients remained alive (Gutman et al, 2015).⁴⁷ Historically, patients with measurable MRD at the time of HSCT have disease relapse rates $>60\%$, and mOS of ~ 1 year. (Walter et al, 2015)⁴⁸ Araki et al, 2016)⁴⁹

1.2.15. Summary of Azacitidine Product Profile

Azacitidine (VIDAZA[®]) is a chemical analogue of the cytosine nucleoside whose mechanism of action involves inhibition of DNA methyltransferase at low doses, causing hypomethylation of DNA, and direct cytotoxicity in abnormal hematopoietic cells in the bone marrow through its incorporation into DNA and ribonucleic acid (RNA) at high doses, resulting in cell death. Azacitidine was approved by the FDA in 2004 for the treatment of all subtypes of MDS according to the FAB classification. Azacitidine was approved in the EU in 2009 for the treatment of adult patients who are not eligible for hematopoietic stem cell transplantation with intermediate-2 and High-Risk MDS (per IPSS), CMML with 10-29% bone marrow blasts without myeloproliferative disorder and AML with 20-30% blasts and multi-lineage dysplasia. In 2015, the EU expanded the approval of azacitidine in AML to include adult patients aged 65 years or older who are not eligible for HSCT with $>30\%$ myeloblasts according to the WHO classification.

1.2.16. Azacitidine Toxicities

Per the VIDAZA[®] EU Summary of Product Characteristics (SPC), the following (very common $\geq 1/10$) adverse reactions associated with azacitidine treatment were obtained from clinical studies and post marketing surveillance: pneumonia, nasopharyngitis, febrile neutropenia, neutropenia, leukopenia, thrombocytopenia, anemia, anorexia, decreased appetite, hypokalemia, insomnia, dizziness, headache, dyspnea, epistaxis, diarrhea, vomiting, constipation, nausea, abdominal pain, petechiae, pruritus, rash, ecchymosis, arthralgia, musculoskeletal pain, fatigue, pyrexia, asthenia, chest pain, injection site erythema, injection site pain, injection site reaction (unspecified), and weight decreased.

1.2.16.1. Azacitidine Dosing Schedule

The dosing schedule in the safety LIC is 75 mg/m²/day SC for 7 consecutive days every 28 days. In the expansion component, azacitidine will be administered per local label or per the Investigational Product Manual (or SPC). Azacitidine may be administered by SC injection or IV infusion at the starting dose of 75 mg/m²/day for 7 days every 28 days. Alternate dosing schedules to administer the 7 doses to accommodate patient and treatment center availability are allowed.

A trial which compared 3 different azacitidine schedules³⁶ showed 44% HI (22/50) for the 5-2-2 dosing schedule (95% CI, 31 to 60), another trial (AZA 001), showed 49% HI in the azacitidine arm (87/177) (p <0.0001). There are no data showing that varying 7 day schedules are not equivalent, therefore, the Investigators can choose the appropriate schedule based on the standard of care at their institution.

1.2.16.2. Azacitidine Dose Modifications

For azacitidine dose modification, refer to the local label or the Investigational Product Manual (or SPC).

Complete information for azacitidine may be found in the SRSD, which for this study is the EU SPC for Vidaza[®].²⁷

1.2.17. Rationale for Testing Glasdegib in Combination with Azacitidine in Patients with Previously Untreated Higher-Risk MDS, AML, and CMML

The combination of glasdegib with azacitidine is proposed for testing in this therapeutic setting based on:

- Clinical and pre-clinical data suggesting a role for aberrant Hh pathway activation in MDS, AML and CMML (See [Section 1.2.2](#) and [1.2.3](#));
- Non-clinical data demonstrating that glasdegib limits LSC proliferation and evidence of glasdegib synergy with chemotherapy (See [Section 1.2.2](#));
- The acceptable safety, tolerability and pharmacokinetic profile observed for glasdegib in clinical studies in patients with hematological malignancies both as a single agent and in combination with decitabine and azacitidine (see [Section 1.2.6](#));
- The clinical activity observed following single-agent and combination treatment with glasdegib in patients with select hematological malignancies (see [Section 1.2.6](#));
- The glasdegib pharmacodynamic data for Hh pathway inhibition obtained in surrogate tissues from a limited number of patients (n=18) with select hematological malignancies and advanced solid tumors (see [Section 1.2.13.2](#)).

The above data along with the high unmet medical need for more effective therapies (higher response rates and hematologic improvement that translate into survival benefit) for patients with higher-risk MDS, AML, and CMML, support the evaluation of glasdegib in combination with azacitidine in this population.

1.2.18. Rationale for the Starting Dose of Glasdegib

As reported in [Section 1.2.13.1](#), the B1371001 study identified the MTD for single-agent glasdegib continuous administration as 400 mg QD, and the RP2D as 200 mg QD in patients with select hematologic malignancies.

Subsequent evaluation of potential dose levels for further studies in patients with hematologic malignancies suggested the 100 mg QD dose level (MTD -4) as the optimal starting dose of single agent glasdegib. This was supported by the following data:

- Clinical benefit observed in 16 patients in the B1371001 study (including some with a diagnosis MDS and CMML) with doses of glasdegib as low as 10 mg QD, with the highest frequency of responses being observed at ≤ 80 mg QD;
- GLI1 (a biomarker of Hh pathway signaling activation) expression is down regulated by $\geq 80\%$ at doses of 50 mg QD and higher in surrogate (skin) tissue, suggesting there will be adequate target modulation at the 100 mg QD dose;
- Potential for increase in glasdegib plasma exposures in the presence of a strong CYP3A4 inhibitor(s) ($\sim 140\%$ increase in AUC_{inf} and a 40% increase in the C_{max}) such as azoles which are medically necessary for management of infections in AML patients.
- Taking into consideration the observed clinical activity, safety and tolerability profile, modulation of hedgehog pathway activity in surrogate tissue, and information relating to the possible impact of a CYP3A4 inhibitor, a dose of 100 mg QD was chosen as the appropriate glasdegib starting dose for further clinical studies both as a single agent and in combination. In the randomized Phase 2 portion of Study B1371003 ([Section 1.2.13.3](#)), clinical benefit was demonstrated with LDAC \pm glasdegib (100 mg Qday continuously in 132 first line AML patients. The mOS was 8.8 months (80% CI: 6.9, 9.9) vs. 4.9 months (80% CI: 3.5, 6.0) for LDAC alone, with a hazard ratio of 0.513 [80% CI: 0.394-0.666]. The safety profile of glasdegib + LDAC was generally tolerable and manageable.
- In the single arm Phase 2 portion of Study B1371003 ([Section 1.2.13.3](#)), for older AML pts receiving intensive chemotherapy, the mOS stratified by subgroup was improved by adding glasdegib. The combination of glasdegib with '7+3' was well-tolerated, with a safety profile consistent with that typically seen in AML patients receiving standard intensive chemotherapy.

These data provides additional rationale for the 100 mg QD dose of glasdegib being a safe and potentially clinically effective dose in combination with azacitidine.

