2.4. Endpoints for the Expansion

Primary Endpoint

- CR rate for MDS patients ([Appendix 2](#)) and AML patients ([Appendix 11](#)).

Secondary Endpoints

- OS;
- For MDS cohort: disease-specific efficacy measures, such as marrow CR (mCR), Partial Remission (PR), Stable Disease (SD), Partial or Complete Cytogenetic Response, and Hematologic Improvement (HI) ([Appendix 2](#));
- For AML cohort: disease-specific efficacy measures, such as CR with Incomplete Hematologic Recovery (CRi), Complete Remission with partial hematologic recovery (CRh), Morphologic Leukemia-Free State (MLFS), PR, and SD ([Appendix 11](#));
- Duration of CR;
- Time to CR;

- Adverse events and laboratory abnormalities as graded by NCI CTCAE v.4.03;
- Pharmacokinetics parameters of glasdegib;
- QTc interval.

CCI

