5.7. Concomitant Treatment(s)

All concomitant medications and treatments must be recorded in the CRF. Any prior treatment received within 28 days prior to study entry (including hematopoietic growth factor receptor agonists: erythropoietin, granulocyte colony stimulating factor (G-CSF), romiplostim, eltrombopag) will be recorded in the CRF.

In addition, any transfusion (red blood cells or platelets) within 8 weeks prior to screening should be recorded in the CRF.

All prior immunosuppressive therapy (eg, cyclosporine) used to treat MDS, or all prior cyto-reduction therapy (eg, hydroxyurea) used to treat AML or CMML, will be recorded regardless of when they were received by the patient. Information collected will include dates of use, best treatment response and the reasons for stopping therapy.

Every concomitant treatment, blood products, growth factors, as well as interventions, required by the patients during the active study treatment (and up to 28 days following last study drug administration or until initiation of another anti-cancer treatment) and the reason for its administration must be recorded on the CRF.

All concomitant medications the patient is currently receiving must be reviewed by the Sponsor prior to enrollment in the safety LIC. Study entry criteria are defined in [Section 4](#).

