9.6. Pharmacokinetic Analysis

9.6.1. PK Parameters

Descriptive statistics will be provided for the following PK parameters in tabular form by analyte, cycle and day: n, mean, SD, CV, median, minimum, maximum, geometric mean and its associated CV.

For the safety LIC, standard plasma PK parameters including the observed maximum plasma concentration (C_{max}), time to maximum plasma concentration (T_{max}), and area under the plasma concentration versus time curve (AUC) for each drug (and metabolite if relevant), will be estimated using non-compartmental analysis. If data permit or if considered appropriate, plasma trough concentration (C_{trough}), average plasma concentration (C_{ave}) will be estimated. For the expansion component, the plasma trough concentration (C_{trough}) will be reported.

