7.3. Pharmacokinetics

Concentrations below the limit of quantification

In all data presentations (except listings), concentrations below the limit of quantification (BLQ) will be set to zero. (In listings BLQ values will be reported as “<LLQ”, where LLQ will be replaced with the value for the lower limit of quantification).

Deviations, missing concentrations and anomalous values

In summary tables and plots of median profiles, statistics will be calculated with concentrations set to missing if one of the following cases is true:

1. A concentration has been reported as ND (i.e., not done) or NS (i.e., no sample),
2. A deviation in sampling time is of sufficient concern or a concentration has been flagged anomalous by the pharmacokineticist.

Note that summary statistics will not be presented at a particular time point if more than 50% of the data are missing.

Pharmacokinetic parameters

Actual PK sampling times will be used in the derivation of PK parameters.

If a PK parameter cannot be derived from a subject’s concentration data, the parameter will be coded as NC (i.e., not calculated). (Note that NC values will not be generated beyond the day that a subject discontinues).

For evaluation of changes in pharmacokinetics of a compound when administered alone vs. in combination, only subjects with matching pair of pharmacokinetic assessments under both conditions will be included in the pharmacokinetic summary (i.e., alone and in combination).

In summary tables, statistics will not be presented for a particular treatment group if more than 50% of the data are NC. For statistical analyses (i.e., analysis of variance), PK parameters coded as NC will also be set to missing.

If an individual subject has a known biased estimate of a PK parameter (due for example to an unexpected event such as vomiting before all drug is absorbed in the body), this will be footnoted in summary tables and will not be included in the calculation of summary statistics or statistical analyses.

[figure not shown]

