8.2.4. Pharmacokinetic Analyses

Analysis Set: PK Analysis set

PK Parameters:

For the safety LIC, standard plasma PK parameters including the observed maximum plasma concentration (C_{max}), time to maximum plasma concentration (T_{max}), and area under the plasma concentration versus time curve (AUC) for each drug (and metabolite if relevant), will be estimated using non-compartmental analysis. If data permit or if considered appropriate, plasma trough concentration (C_{trough}), average plasma concentration (C_{ave}) will be estimated.

For the expansion cohorts, the plasma trough concentration (C_{trough}) will be reported.

Presentation of pharmacokinetic data will include:

- Descriptive statistics (n, mean, SD, %CV, median, minimum, maximum) of plasma concentrations for PF-04449913 and azacitidine will be presented in tabular form by treatment cohort, dose level, cycle, day and nominal time.
- In the Phase 1b safety Lead-in, linear and semi-log plots of mean and median plasma concentrations by nominal time for PF-04449913 and azacitidine will be presented for PK sampling days by cycle, study day, and by treatment. Similar plots will be presented for each individual patient concentrations.
- Pharmacokinetic parameters (as treated and dose compliant groups) PF-04449913 and azacitidine will be listed and summarized by treatment cohort/dose level and study day using descriptive statistics (n, mean, SD, %CV, median, minimum, maximum, and geometric mean and its associated %CV). PK parameters with zero values will be excluded from the calculation of geometric means and its associated %CV. If an intra patient dose escalation or reduction occurs, data for that patient will only be included in descriptive statistics and summary plots up to the time of the dose change.
- Matchstick plots for C_{max} and AUC for PF-04449913 and azacitidine for the drug-drug interaction analysis dataset.

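### Expansion glasdegib Ctrough is summarised without separating samples taken on and off CYP3A4/5 inhibitors, although the protocol's own figures imply a strong inhibitor raises the trough about 2.8 to 3.0 times

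*Protocol*

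**What the plan says.** Protocol 2.4 lists "Pharmacokinetics parameters of glasdegib" among the secondary endpoints of the expansion. The analysis sections narrow this to one parameter. Protocol 9.6.1 says: "For the expansion component, the plasma trough concentration" will be reported. SAP 8.2.4 says the same: "For the expansion cohorts, the plasma trough concentration". Both sections assign Cmax, Tmax and AUC to the lead-in cohort. The Statistical Methods part of the Protocol Summary names those three without that limit.

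Under SAP 8.2.4, PK parameters are summarised by cohort or dose level and study day, and plasma concentrations "will be presented in tabular form by treatment cohort, dose level, cycle, day and nominal time". Protocol 9.6.2 uses cycle, day and nominal time. None of these lists includes inhibitor use. SAP 8.2.4 does handle one change in exposure explicitly: after an intra-patient glasdegib dose change, the patient's later data leave the descriptive statistics.

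Protocol 1.2.18 puts the effect of a strong CYP3A4 inhibitor at about +140% on AUC and +40% on Cmax, and describes such inhibitors with the words "such as azoles which are medically necessary for management of infections in AML patients". Protocol 5.7.1 restates the effect for ketoconazole as 2.4-fold and 1.4-fold. It advises against moderate and strong inhibitors but allows them, with caution, when medically necessary. Protocol 5.7.2.1 lists anti-fungal agents as supportive therapy. Protocol 5.7 states: "All concomitant medications and treatments must be recorded in the CRF". Population PK (protocol 9.6.4, SAP 8.2.4.2) is optional and names no covariate.

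**The concern.** A trough is the part of the concentration profile most sensitive to slower clearance. If samples taken under strong inhibition sit in the same 100 mg row as the others, the mean and CV of that row depend partly on how many patients happened to take such a drug. A reader could not tell whether a high or variable Ctrough reflects glasdegib itself or co-medication. If use differs between the AML and MDS cohorts, a difference in Ctrough between them could reflect that use.

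The SAP's own handling of dose changes points the same way. Exposure is described as generally dose-proportional (protocol 1.2.11), so a change from 100 mg to 50 mg alters it by a factor of 2, and the SAP removes the later data. A strong inhibitor moves the trough by more than 2, and those samples stay in the row unmarked.

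**Working it through.** **Inputs.** AUC +140% and Cmax +40% with a strong inhibitor (protocol 1.2.18); 2.4-fold and 1.4-fold with ketoconazole (protocol 5.7.1). Half-life 17.4 to 34.3 h, about 24 h at most dose levels; accumulation ratio 1.2 to 2.5; Vz/F 185 to 455 L; multiple-dose CL/F 5.33 to 13.3 L/h; multiple-dose AUCtau geometric CV 10% to 61% (all protocol 1.2.11). Dosing interval 24 h.

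**1. The stated figures agree.** 1 + 1.40 = 2.4 and 1 + 0.40 = 1.4, so 1.2.18 and 5.7.1 match. The documents state no trough ratio; it has to be derived.

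**2. Is a one-compartment model reasonable?** With k = ln2 / half-life, predicted accumulation is 1/(1 − e^(−24k)). This gives 1.62 at 17.4 h, 2.0 at 24 h and 2.6 at 34.3 h, against a stated 1.2 to 2.5. Half-life from volume and clearance is ln2 × 185/5.33 = 24.1 h and ln2 × 455/13.3 = 23.7 h. Both checks are close enough for this purpose.

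**3. Trough ratio.** At steady state the trough is proportional to F × e^(−24k)/(1 − e^(−24k)). At 24 h, k = 0.0289 and the off-inhibitor value is 0.5/0.5 = 1.0.

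- A, all of the effect is lower clearance: k/2.4 = 0.0120, and 0.749/0.251 = 2.99.
- B, F × 1.4 and clearance ÷ (2.4/1.4 = 1.71): k = 0.0168, and 1.4 × 0.667/0.333 = 2.81.

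| Half-life | A | B |
|---|---|---|
| 17.4 h | 3.27 | 3.00 |
| 24 h | 2.99 | 2.81 |
| 34.3 h | 2.79 | 2.67 |

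With first-order absorption (Tmax 1, 2 or 4 h) and a 24 h half-life, A gives 2.93 to 2.98. B, refitted to match both stated ratios, gives 2.79 to 2.81. A alone would raise single-dose Cmax by only 1.02- to 1.06-fold, so B fits the stated figures better, and 2.8 is used below. Putting the whole effect into F would give a trough ratio of 2.4, but that needs Cmax × 2.4, which the stated 1.4 excludes.

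**4. Effect on a pooled row.** Let f be the share of samples on a strong inhibitor. The documents do not give f, so 10% to 30% is an assumption. The within-stratum CV is assumed to be 40%, so σ² = ln(1 + 0.40²) = 0.148. Relative to the off-inhibitor value:

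- geometric mean = 2.8^f;
- arithmetic mean = 1 + 1.8f;
- median = e^x, where (1 − f)Φ(x/σ) + fΦ((x − ln 2.8)/σ) = 0.5;
- pooled geometric CV = √(exp(σ² + f(1 − f)(ln 2.8)²) − 1).

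| f | Geometric mean | Arithmetic mean | Median | Pooled CV |
|---|---|---|---|---|
| 10% | 1.11 | 1.18 | 1.055 | 53% |
| 20% | 1.23 | 1.36 | 1.128 | 61% |
| 30% | 1.36 | 1.54 | 1.234 | 67% |

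**5. How many samples.** Protocol Table 4 with its footnote 3 schedules two pre-dose PK samples per patient, at Cycle 1 Day 15 and Cycle 2 Day 1. With about 30 patients per cohort, six patients on a strong inhibitor make 20% of a row.

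**The case against.** The other side has several good arguments, and most of them limit the point rather than remove it.

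- **Pooling is inferred from silence.** SAP 6.3.1 (PK Endpoints) appears in the contents, but its text is not in the available copy. Some PK text is redacted, and SAP 8.2.4 mentions as-treated and dose-compliant groups that the visible text does not define. A rule could exist there. This stands.
- **A reader might infer that any inhibitor triples the trough, or that azole use is certain to be common in AML.** The documents support neither. The figures are for a strong inhibitor, and Appendix 7 lists fluconazole, an azole, as moderate with no interaction figure. Section 5.7.1 advises against these drugs, so the share affected is unknown.
- **A reader might infer that a false AML-versus-MDS difference will appear.** The documents do not compare expected use in the two cohorts, and no PK comparison between cohorts is visible. If use did differ, the exposure difference would be real; only its cause would be unclear.
- **A reader might infer that the SAP will discard inhibitor-driven values.** SAP 7.3 sets values to missing when "a concentration has been flagged anomalous by the pharmacokineticist". It gives no criterion and mentions neither high values nor inhibitors, so this is a possibility only.
- **A reader might want inhibitor-free samples as the main summary.** That is a choice of target, not a correction. Section 1.2.18 considered the possible impact of an inhibitor when choosing 100 mg, so exposure as actually used is a legitimate description. Restricting to inhibitor-free samples would select patients who did not need such treatment.
- **Nothing is lost.** Individual concentrations are presented and co-medication is recorded, so a later split is possible. The planned exposure-QTc model uses measured concentrations, not the Ctrough table. This is true, but a split chosen after seeing the data is weaker than one written down now.

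**Conclusion.** The point holds in a limited form. In the visible text, expansion Ctrough is summarised across samples taken on and off CYP3A4/5 inhibitors. By the protocol's own figures a strong inhibitor would raise the steady-state trough about 2.8 to 3.0 times at a 24 h half-life, and 2.7 to 3.3 times over the stated range. At ratio 2.8, if 10% to 30% of samples are affected, the pooled geometric mean rises by about 11% to 36% and the median by about 5.5% to 23%. The CV goes from an assumed 40% to between 53% and 67%.

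This rests on linear one-compartment kinetics, on a single-dose AUC ratio carried over to steady state, and on the assumed share and CV. The implied half-life under inhibition is 41 h (24 × 1.71) to 58 h (24 × 2.4), so a sample taken soon after an inhibitor is started would show less than the full ratio. Nothing can be said about the size for moderate inhibitors.

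The endpoint is secondary and descriptive. The CR rate, the futility and safety stopping rules and the concomitant-medication rules are untouched. The change is worth making because it is cheap, not because the study's main conclusions are at risk.

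**What to change.** In SAP 8.2.4, with matching wording in protocol 9.6.1 and 9.6.2:

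1. Classify each expansion glasdegib PK sample as no, moderate or strong CYP3A4/5 inhibitor (Appendices 6 and 7) from the CRF medication dates. The pharmacokineticist should set the look-back window before the analysis.
2. Report Ctrough by that status in addition to the planned all-sample summary, with the number of samples in each row.
3. In SAP 7.3, state that a value is not flagged anomalous solely because it is high when a recorded inhibitor explains it.

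If SAP 6.3.1 already contains such a rule, a cross-reference in 8.2.4 is enough. The cost is SAP and protocol wording and one table stratum; the data are already collected. The drawback is small rows: with two scheduled troughs and about 30 patients per cohort, an inhibitor row may hold only a handful of patients and should be read as descriptive. No dosing or co-medication rule changes.
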